## C. Characterization procedures

The procedures that subjects will undergo at each study visit are shown in Appendix 1. The procedures include the following:

**Questionnaires.** Questionnaires will be administered which assess the clinical, environmental and medication history of the subjects. In addition, questions will be asked on work environment and days lost from work/school. Separate questionnaires will be completed related to asthma quality of life (AQLQ®/PAQLQ®) and asthma control (ACQ®, ACT®/cACT®). Additional supplemental validated questionnaires will be administered at certain visits. These include questionnaires about sleep [Epworth sleepiness scale®, Insomnia Severity Index® (ISI)], depression, anxiety, and stress [Hospital Anxiety and Depression Scale® (HADS)], medication adherence [Medication Adherence Report Scale® (MARS)], and sugary beverage consumption (Beverage Questionnaire (BEVQ-15).

**Asthma Exacerbation Questionnaire.** In addition to the questionnaires administered by phone and in-person, participants will be asked to complete an online questionnaire about asthma control and exacerbations. Given the relative paucity of available instruments to assess details about asthma exacerbation, we are testing several questions already developed for 6 month recall in the SARP LP for use on a monthly/per exacerbation basis. The questionnaire is hosted by Qualtrics through the UCSF platform. Participants may opt-out at the time of their initial study consent or at any time during their participation. Participants will be sent a monthly reminder emails (provided at enrollment) with an individualized link to the exacerbation questionnaire. Participants will also be asked (and reminded by stickers placed on their rescue inhalers) to complete the questionnaire again if they are actively experiencing or have recently experienced an asthma exacerbation. (see Online Exacerbation Survey MOP).

**Physical Examinations.** Physical examinations will include a determination of vital signs and evaluation of the lungs, cardiovascular system, and a nasal-oropharyngeal examination. Tanner staging will also be performed in children (see Growth MOP)

**Vital Signs.** Vital signs such as blood pressure and temperature will be taken as well as height and weight. Hip and waist circumference will also be measured.

**Venipuncture.** Venipuncture will be performed for cellular differentials, IgE levels, cytokines, chemokines, metabolic measures, inflammatory cells, PAXgene, and other inflammatory mediators (see Biospecimen MOP). A blood sample will be collected to isolate DNA to evaluate human genes (DNA) and how they may be related to the development of asthma, allergy, respiratory and related diseases. As part of the genetic study, a sample of DNA may have Genome Wide Association Studies (GWAS) or Whole Genome Sequencing (WGS) performed (see Biospecimens MOP).

**Spirometry.** Spirometry will be performed to assess airflow limitation (see Spirometry MOP).

**Maximum Bronchodilation.** Maximum bronchodilation will be performed with spirometry to assess bronchodilator reversibility. Subjects will receive 4 inhalations of albuterol from a metered dose inhaler (MDI) and valved holding chamber and spirometry will be repeated 15 minutes later. The subject will then be administered an additional 2 puffs of an albuterol MDI and spirometry will be repeated after 15 minutes. The difference in the FEV1 after 2 puffs will be compared to the difference in FEV1 after 4 puffs. If the difference is greater than 5%, 2 more puffs of albuterol MDI will be administered and spirometry measured after 15 minutes. If the difference is less than 5%, the procedure will be stopped. No more than 8 puffs total of albuterol MDI will be given (see Spirometry MOP). Adult participants (age 18+) who do not reverse  $\geq 12\%$  for study qualification may additionally be given 4 puffs ipratropium bromide (Atrovent® HFA) and spirometry will be repeated 30 minutes later. Several studies support additional bronchodilation with albuterol and ipratropium given concurrently, even in patients with preserved lung function (Gelb et al. 2008 Pulm Pharmacol Ther 21(4):630-6). Ipratropium is an anticholinergic bronchodilator that is FDA approved for the treatment of chronic bronchitis, emphysema and chronic obstructive pulmonary disease (COPD). Although ipratropium has not been FDA-approved for use in asthma, it is widely used for asthma, and an NIH Task Force (Tepper et al. 2012 J Allergy Clin Immunol 129(3 Suppl:S65-87) and US and International guidelines (Miller et. Al. 2005 Eur Resp J 26(2):319-38) all recommend ipratropium in this dose for characterization of asthma.

**Methacholine Challenge.** Only subjects with a pre-diluent FEV1 of  $>50\%$  predicted ( $>70\%$  in children aged 6 to 17 years) and at least 1.0 liter (if adults) will undergo methacholine testing. A physician will be available during the challenge. Testing will be initiated with diluent only followed by the lowest concentration of methacholine. Study staff will calculate and record the FEV1 value that equals both a 10% and 20% fall in FEV1 based upon the recorded diluent FEV1, and subjects will not be discharged until their FEV1 is within 10% of their pre-diluent FEV1 (see Methacholine MOP).

**Exhaled nitric oxide.** Exhaled nitric oxide is a non-invasive procedure that is considered to be an indirect measurement of airway inflammation. Subjects will be instructed to take in a deep breath and blow air out at a constant pressure as directed by personnel. One measurement will be taken and recorded (see Exhaled Nitric Oxide MOP).

**Urine Collection.** Clean catch urine will be collected for oxidative metabolite analysis. If the subject is a female of child-bearing potential, a urine pregnancy test will be conducted at all visits to exclude pregnancy prior to administration of study medications or performance of certain study procedures (see Urine Biospecimen MOP).

**Exhaled Breath Condensate.** Exhaled breath condensate is a noninvasive collection of nongaseous components of the expiratory air. After putting on nose clips, subject will put mouthpiece in mouth and breathe normal tidal breathing for 10-15 minutes. Exhaled air will pass through a cold metal tube where the liquid particle condenses and collects in a small collection tube. The subject can interrupt the procedure any time to cough, sneeze or spit out saliva and when ready resume tidal breathing through the mouthpiece. When collection time has ended the sample collection vessel is removed immediately (see Exhaled Breath Condensate MOP).

**Sputum Induction.** Sputum cells and fluid phase will be saved for assessment of lower airway inflammation and presence of respiratory pathogens. The following safety procedures will be followed for the sputum induction procedure; all subjects will be pre-treated with 4 puffs of albuterol pre-induction and only subjects (aged 12 and above) with a post bronchodilator FEV1 of >50% predicted (>70% in children aged 12 to 17 years) will undergo sputum induction. Spontaneous sputum samples may be collected on subjects with an FEV1 below these limits. A physician will be available during the challenge; study staff will calculate and record the peak flow and FEV1 value that equals both a 10% and 20% fall in lung function based upon the recorded post-bronchodilator peak flow and FEV1 values and subjects will not be discharged until their FEV1 is within 10% of their post bronchodilator FEV1 (see Sputum MOP).

**Corticosteroid administration.** Each subject that meets inclusion/exclusion criteria will receive triamcinolone acetonide intramuscularly at the end of visit 2. Adults  $\geq 18$  years will receive 40 mg triamcinolone acetonide. Children 6-17 years will receive 1 mg/kg triamcinolone acetonide (up to 40 mg maximum). Triamcinolone acetonide will be administered as a single intramuscular dose deep in the gluteal region. Visit 2 will be timed so that the triamcinolone injection is not given within 4 weeks of the administration of any live attenuated vaccine.

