#### **A. Inclusion criteria**

A diverse sample of subjects with asthma is needed to gain better understanding of asthma and its endotypes. SARP will therefore enroll subjects 6 years and older with a physician diagnosis of asthma. The target recruitment goal for each center is 75% adults (age 18 and older) and 25% children age 6-17 years. Within the pediatric age group, an attempt will be made to enroll equal numbers of children 6-11 and 12-17 years of age. Similarly, an attempt will be made to enroll at least 50% females and 30% minorities. Each center will enroll approximately 100 subjects over the first three years of the grant award in order to study them longitudinally for up to six years. Subjects from SARP I and II may be enrolled in SARP III, but at least 50% of all subjects at each center should be newly recruited to SARP III.

Because there are a number of respiratory disorders that may be confused with asthma or confound asthma assessment, to be eligible for the longitudinal phase of the study, SARP

enrollees must demonstrate FEV1 bronchodilator reversibility  $\geq 12\%$  or airway hyperresponsiveness reflected by a methacholine PC20  $\leq 16$  mg/mL (Historical methacholine data from previous NIH trial [SARP I or II, AsthmaNet, ALA-ACRC, KIA, ACRN or CARE] will be allowed). An exception will be made for enrollees whose FEV1 is  $< 50\%$  predicted ( $< 70\%$  in children aged 6 to 17 years), precluding methacholine challenge testing. If bronchodilator reversibility is  $< 12\%$  in these participants, a diagnosis of asthma acceptable to the investigator is sufficient for inclusion in SARP.

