#### D. Visit-specific procedures

##### Visit 1 – Approximately 2.0 hrs

Visit 1 is set up as a consenting visit. The coordinator will present a detailed review of the SARP consent and answer any questions regarding the study and study procedures.

This consent describes the national SARP group and the collective/common procedures, data sharing, sample sharing and genetic blood draw. A detailed medical and asthma history will be taken. Subjects will be given a brief physical examination that includes vital signs, height, weight, BMI and Tanner staging for children under the age of 17 (see Growth MOP). Subjects will also complete questionnaires (ACT/cACT, ACQ, and AQLQ/PAQLQ) and additional validated questionnaires. Females of childbearing potential will have a urine pregnancy test.

Baseline spirometry will be performed in all age groups. Spirometry will be performed before and after albuterol for all age groups and possibly ipratropium bromide for adults to determine maximum reversibility. A maximal reversibility must be completed within 6 weeks of Visit 2, either performed at this visit or at Visit 2.

If the subject has a previously documented methacholine challenge performed according to standard procedures from an NIH trial (SARP I or II, AsthmaNet, ACRN, or CARE), or the ALA-ACRC, he/she will not need to complete a methacholine challenge procedure.

Visit 1 can be split into several visits to complete screening based on site specific SOPs.

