## **B. Monitoring of adverse events related to the study**

The occurrence of an AE may come to the attention of study personnel during study visits or telephone interviews or by a patient presenting for medical care. The following AEs are expected from participation in the study.

**Blood draw:** Subjects may experience some lightheadedness or nausea while having blood drawn. There is a risk of bruising at the site where the needle enters the skin and a remote risk of infection.

**Spirometry and maximum bronchodilation:** Subjects may experience shortness of breath while doing spirometry, and very rarely, syncope. Temporary wheezing and chest tightness infrequently (5% of the time) occur. Following the bronchodilator, there is likely (>25% chance) to be a transient increase in heart rate and tremor. Adults taking 4 puffs of ipratropium (Atrovent® HFA) for this test may experience headache, dry mouth, nausea, bronchitis, and shortness of breath. These side effects were reported in patients with COPD who took ipratropium for 12-weeks [Boehringer Ingelheim Pharmaceuticals, Inc. USPI, Revised 8/2012]. Since participants will only take ipratropium once, the likelihood of these side effects is much less. These side-effects are non-life threatening and are short-lived.

**Methacholine Challenge:** Subjects may experience shortness of breath, coughing, lightheadedness and dizziness. In rare cases, some patients have experienced a severe asthma attack or a reaction to the methacholine. Subjects with a pre-diluent FEV1 of >50% predicted (>70% in children aged 6 to 17 years) and at least one liter will undergo the methacholine testing if they do not have a historical methacholine from a previous NIH trial (CARE, AsthmaNet, SARP I or II, or ACRN) and a physician will be available during the challenge. Subjects will not be discharged until their FEV1 is within 10% of their pre-diluent FEV1.

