## VII. Appendix 1: Table of Procedures in Longitudinal Protocol

Minimum Procedure Set	Characterization			Longitudinal Follow-up						Long-term Extension		
	Baseline	Steroid Responsiveness		6 mos 	12 mos	18 mos 	24 mos	30 mos 	36 mos	Annual PC 	Annual clinic visit	
	V1 	V2 (pre)	V3 (post)		V4		V5		V6		V7	V8-V9
Visit scheduling window (6 month to V6 calculated from time of enrollment)		Max BD must be w/in 6 weeks of V2	18 ± 3 days from V2	6 mos ± 60 days	12 mos ± 90 days	18 mos ± 60 days	24 mos ± 90 days	30 mos ± 60 days	36 mos ± 90 days	± 60 days	48 mos ± 90 days	± 90 days
Consent and eligibility	X											
SARP 3 Questionnaires	X			X	X	X	X	X	X	X	X	X
Validated questionnaires 	X	X	X	X	X	X	X	X	X	X	X	X
Physical exam/VS/Hgt/Wgt/BMI	X				X		X		X		X	X
Tanner staging												
Spirometry	X	X	X		X		X		X		X	X
Max bronchodilation	X 	X 	X		X		X		X		X	X
Methacholine	X 											
Urine pregnancy test	X	X	X		X		X		X		X	X
Urine collection		X	X		X		X		X		X	
Sputum induction (ages 12 and above)		X	X		X							X
Exhaled nitric oxide		X	X		X		X					X
Exhaled breath condensate		X	X		X		X		X			X
Blood sample – CBC		X	X						X		X	X 
Blood sample – DNA / RNA (Paxgene)		DNA	DNA						RNA			Both 
Blood sample – Serum, plasma		X	X		X		X		X		X	X 
Blood sample – HbA1c, cholesterol, HDL, triglycerides, glucose (fasting), insulin (fasting)									X			
ImmunoCap (includes IgE)		X										
Corticosteroid treatment 		X										
Online Asthma Exacerbation Ques.	Monthly or as exacerbations occur											

Testing in V1 may be completed on several days as determined by individual site standard operating procedures. Specific Validated Questionnaires are detailed in the MOP.

Maximal reversibility must be completed within 6 weeks of V2, either at V1 or V2. It must be repeated at V2 if medications change after V1 procedure. Adults who do not reverse ≥12% for study qualification may additionally be given 4 puffs ipratropium bromide MDI, with spirometry repeated 30 minutes later. Methacholine challenge will be performed only if subject does not have a previously positive methacholine challenge (as defined in MOP). Treatment administered at end of visit 2. Subject contact by telephone only (PC=Phone Call). At either Visit 8 or Visit 9.

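### The FEV1 limits for the methacholine challenge differ between Sections III.C and IV.B, the eligibility exception in III.A does not cover everyone those limits bar, and the waiver for prior tests is worded in conflicting ways

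*Combined protocol and SAP*

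**What the plan says.** Five places in the protocol bear on who receives a methacholine challenge and what follows for eligibility.

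- **Section III.C, Methacholine Challenge.** Only people with a pre-diluent FEV1 above 50% predicted (above 70% at ages 6 to 17) "and at least 1.0 liter (if adults) will undergo methacholine testing".
- **Section IV.B, Methacholine Challenge.** The same percent limits, then "and at least one liter will undergo the methacholine testing if they do not have a historical methacholine from a previous NIH trial". No age limit is attached to the litre.
- **Section III.A, Inclusion criteria.** Enrollees must show reversibility of at least 12% or a PC20 of at most 16 mg/mL, and historical methacholine results from named sources count. "An exception will be made for enrollees whose FEV1 is" below 50% predicted (below 70% at ages 6 to 17), a level described as "precluding methacholine challenge testing". For them, if reversibility is under 12%, a diagnosis acceptable to the investigator is enough.
- **Section III.D, Visit 1.** With a documented prior challenge from a listed source, "he/she will not need to complete a methacholine challenge procedure". The result of that test is not mentioned.
- **Appendix 1, footnote 4.** The challenge is done "only if subject does not have a previously positive methacholine challenge", with the definition left to the MOP.

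**The concern.** The FEV1 floor is a safety limit for a procedure that, according to Section IV.B, can in rare cases provoke a severe asthma attack. The opening of Section III promises standardized procedures and uniform safety precautions at all centers. If III.C and IV.B differ, two centers can each follow the protocol and treat the same child differently.

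The same limits also feed eligibility. The exception in III.A exists because some people cannot be challenged, yet its definition leaves out some of the people whom the testing rules bar. A person with a lower percent-predicted FEV1 can then enter on the investigator's diagnosis, while a person slightly above the cut-off, equally unable to be challenged, cannot.

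The waiver wording leaves a further question open: whether someone whose prior test was negative is to be tested again.

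**Working it through.** The protocol states no figure to reproduce. The check sets the rules side by side and runs illustrative cases through them.

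**Rules**

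- Testable under III.C: FEV1 above 50% predicted (child: above 70%) and, for adults only, at least 1.0 L.
- Testable under IV.B: the same percent limits and at least 1 L at any age.
- Excepted under III.A: FEV1 below 50% predicted (child: below 70%). There is no litre criterion.

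**Cases** (values chosen for illustration; reversibility under 12% and no prior test assumed)

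| Case | Testable, III.C | Testable, IV.B | Excepted, III.A |
|---|---|---|---|
| Adult, 45%, 1.2 L | no | no | yes |
| Adult, exactly 50%, 1.3 L | no | no | no |
| Adult, 55%, 0.95 L | no | no | no |
| Adult, 60%, 1.6 L | yes | yes | no |
| Child, 65%, 0.9 L | no | no | yes |
| Child, exactly 70%, 1.1 L | no | no | no |
| Child, 75%, 0.95 L | yes | no | no |
| Child, 80%, 1.2 L | yes | yes | no |

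In only one row do the two testing rules disagree: the child above 70% and under 1.0 L. Three further rows are neither testable nor excepted: the adult under 1.0 L and the two boundary cases. The child at 75% joins them if IV.B governs.

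**Who can fall in the litre gap.** FEV1 must exceed p × predicted and be below 1.0 L, so predicted FEV1 must be below 1.0 / p.

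- Adult: 1.0 / 0.50 = 2.0 L.
- Child: 1.0 / 0.70 = 1.43 L.

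**Size of the pediatric group.** The target is 700 subjects, 25% of them children, with an attempt at an equal split between ages 6 to 11 and 12 to 17: 700 × 0.25 = 175, and 175 / 2 = 87.5. So roughly 87 children aged 6 to 11 are planned. The documents give no FEV1 distribution, so the share under 1.0 L is unknown.

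**Waiver.**

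| Place | Result required of the prior test | Sources named |
|---|---|---|
| III.D, Visit 1 | none stated | SARP I or II, AsthmaNet, ACRN, CARE, ALA-ACRC |
| IV.B | none stated | SARP I or II, AsthmaNet, ACRN, CARE |
| Appendix 1, footnote 4 | positive | none named; refers to MOP |

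A person with a negative test from a source on both lists is relieved of the challenge by the first two rows and not by the third. The source lists also differ. Counting SARP I and II as one source, III.A accepts six as evidence for eligibility, including KIA. Visit 1 lists five and IV.B four.

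**The case against.** **Section III.C is the operative procedure.** It is worded restrictively and cites the Methacholine MOP, while IV.B is a description of risks. That is a fair reason to look to III.C first, and the MOP, which is not among the documents, may settle some points. It does not remove the discrepancy. IV.B reads as a restatement of the safeguards: the sputum-induction limits agree between the two sections, age bands included, and the methacholine limits do not. Both sections do keep the 70% limit for children, a physician available, and no discharge until FEV1 is within 10% of its pre-diluent value.

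**Other routes into the study exist.** This stands and limits the point. Reversibility of 12% carries no minimum volume; at 0.95 L it is 0.12 × 950 = 114 mL. It is assessed after up to 8 puffs of albuterol and, for adults still below 12%, possibly ipratropium. An accepted historical test also qualifies. All of these must fail before anyone is shut out.

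**The boundary cases are a drafting matter.** Largely so. They matter in practice mainly if percent predicted is recorded in whole numbers, which the documents do not say.

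Three stronger readings are tempting, and the documents do not support them.

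- A reader might infer that any participant could be tested, barred or excluded depending on the page. That sequence fits only children above 70% and under 1.0 L. For adults, III.C and IV.B agree.
- A reader might infer that a negative prior test means never being tested and so never qualifying. Visit 1 lifts an obligation; it does not forbid a new challenge. III.A can also be read as accepting historical data only as evidence of a qualifying result. The texts leave the matter unclear rather than dictate exclusion.
- A reader might infer that the fixed-obstruction end of the cohort is lost. III.A expressly admits those with the lowest percent-predicted FEV1. The adults left out by the litre floor have a predicted FEV1 below 2.0 L, which reflects small predicted lung size as much as severity.

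**Conclusion.** The point holds in three limited parts. First, III.C and IV.B contradict each other on whether the litre floor applies to children. Second, the III.A exception falls short of its own stated purpose; this is a gap, not a contradiction, and it closes the door only on people with reversibility under 12% after maximal bronchodilation and no qualifying historical test. Third, the waiver texts differ on whether the prior test must be positive.

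The number affected is probably small and cannot be computed from the documents. The challenge is scheduled only at Visit 1. Enrollment was planned for the first three years of the award, and the text is V12.0 dated 10/16/2019 with extension visits, so enrollment had probably closed; that is an inference. The point is worth correcting because it concerns a safety limit and an entry criterion, but nothing here shows that the cohort is materially distorted.

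**What to change.** Reconcile Sections III.C and IV.B to one set of FEV1 limits by age group. Define the III.A exception by reference to those limits, so that everyone barred from the challenge on FEV1 grounds falls under one rule, with no gap at the boundary. Make Visit 1, Section IV.B and Appendix 1 footnote 4 agree on which prior tests waive the challenge, covering both the result required and the accepted sources, and align them with the source list in III.A and with the Methacholine MOP. Which limits and which waiver rule apply is for the sponsor and investigators to decide.

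The cost is protocol wording only. If enrollment has closed, record which rule the sites applied, so that analysts know how participants were tested and admitted.
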